2.4.1.1. Power to Show Superiority in mean SSP AIM/IAM/FIM scores

Table A shows preliminary AIM/IAM/FIM data from the ongoing U.S. implementation study CUSTOMIZE (209493).

Table A Staff Study Participants Scores at Month 4 in CUSTOMIZE (209493)

	N	Mean	SD	Median	Observed Range (min-max)	Floor n (%)	Ceiling n (%)	Skewness	Kurtosis
AIM Scale (Total Sample)	24	4.39	0.61	4.13	3.25-5.00	0 (0.0%)	11 (45.8%)	-0.16	-1.58
IAM Scale (Total Sample)	24	4.45	0.59	4.50	3.25-5.00	0 (0.0%)	12 (50.0%)	-0.34	-1.39
FIM Scale (Total Sample)	24	4.32	0.71	4.25	3.00-5.00	0 (0.0%)	11 (45.8%)	-0.47	-1.09

Based on these preliminary data from CUSTOMIZE study, and the given sample size (the number of study participants), the power to detect a difference of 0.5 between the implementation arms in terms of AIM, IAM and FIM in line with our primary hypothesis are shown in Table B.

Table B Power to Detect a 0.5 Difference in AIM/IAM/FIM

Endpoint	ARM-S	ARM-E	Delta	SD	Alpha	N(S)	N(E)	Power*
AIM	4.39	4.89	0.5	0.61	0.05	27	27	84%
						36	36	93%
IAM	4.45	4.95	0.5	0.59	0.05	27	27	86%
						36	36	94%
FIM	4.32	4.82	0.5	0.71	0.05	27	27	72%
						36	36	84%

*Power calculation using two-sided T-test assuming equal variance.

As shown in Table B, with 27 study staff participants (3 per site) surveyed on each arm, the study would have 72%-86% power to detect a 0.5 difference in FIM, AIM and IAM endpoints between ARM-E (Enhanced implementation strategy arm) and ARM-S (Standard implementation arm) assuming data from Table A (CUSTOMIZE study) for ARM-S.

And with 36 study staff participants (4 per site) surveyed on each arm, the study would have 84% - 94% power to detect a 0.5 difference in FIM, AIM and IAM endpoints between ARM-E and ARM-S.

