9. STATISTICAL CONSIDERATIONS

9.1. Statistical Hypotheses

The hypotheses on the quantitative aspects of this study is that enhanced implementation strategy is superior than the standard implementation strategy in terms of mean staff study participant (SSP) AIM/IAM/FIM scores. i.e.,

 H_0 : μ (enhanced) = μ (standard) vs. H_1 : μ (enhanced) > μ (standard)

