9.2. Sample Size Determination

The study size is based on practical considerations in terms of feasibility of enrolling an adequate number of sites on each implementation strategy balanced with the desire to have interventions tested across several types of investigative sites; as well as enrolling an adequate number of patient study participants in each site.

Approximately 24 sites (from feasibility process) will be selected from the feasibility process to achieve 18 sites randomly assigned to study implementation strategies and approximately 54 evaluable staff study participants for an estimated total of 27 evaluable study staff participants per implementation strategy group.

Assuming 10% screen failures, it is estimated that with 18 sites approximately 527 patient study participants will be screened to achieve 474 subjects enrolled and 450 evaluable patient study participants completing the study (assumes 5% of patient study participants would be non-evaluable) for an estimated total of 225 evaluable patient study participants per implementation strategy group.

Power to Show Superiority in mean SSP AIM/IAM/FIM scores

Table 10 shows preliminary AIM/IAM/FIM data from the ongoing U.S. implementation study CUSTOMIZE (209493).

	N	Mean	SD	Median	Observed Range (min-max)	Floor n (%)	Ceiling n (%)	Skewness	Kurtosis
AIM Scale (Total Sample)	24	4.39	0.61	4.13	3.25-5.00	0 (0.0%)	11 (45.8%)	-0.16	-1.58
IAM Scale (Total Sample)	24	4.45	0.59	4.50	3.25-5.00	0 (0.0%)	12 (50.0%)	-0.34	-1.39
FIM Scale (Total Sample)	24	4.32	0.71	4.25	3.00-5.00	0 (0.0%)	11 (45.8%)	-0.47	-1.09

Table 10Staff Study Participants Scores at Month 4 in CUSTOMIZE (209493)

Based on these preliminary data from CUSTOMIZE study, and the given sample size (the number of study participants), the power to detect a difference of 0.5 between the implementation arms in terms of AIM, IAM and FIM are shown in Table 11.

Table 11 Power to Detect a 0.5 Difference in AIM/IAM/FIM

Endpoint	ARM-S	ARM-E	Delta	SD	Alpha	N(S)	N(E)	Power*
AIM	4.39	4.89	0.5	0.61	0.05	27	27	84%
						36	36	93%

Endpoint	ARM-S	ARM-E	Delta	SD	Alpha	N(S)	N(E)	Power*
IAM	4.45	4.95	0.5	0.59	0.05	27	27	86%
						36	36	94%
FIM	4.32	4.82	0.5	0.71	0.05	27	27	72%
						36	36	84%

*Power calculation using two-sided t-test assuming equal variance.

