As shown in Table 11, with 27 study staff participants (3 per site) surveyed on each arm, the study would have 72%-86% power to detect a 0.5 difference in FIM, AIM and IAM endpoints between ARM-E (Enhanced implementation strategy arm) and ARM-S (Standard implementation arm) assuming data from Table 10 (CUSTOMIZE study) for ARM-S.

And with 36 study staff participants (4 per site) surveyed on each arm, the study would have 84% - 94% power to detect a 0.5 difference in FIM, AIM and IAM endpoints between ARM-E and ARM-S.

Sample Size for Provider Population

An overall average number of 9 sites, per arm, would produces a two-sided 95% confidence interval with a distance from the mean paired difference (e.g. site level mean change from baseline in AIM, IAM or FIM score) to the limits (half-width) that is equal to 0.497 when the estimated standard deviation of the paired differences is 1.0, across sites.

Table 12Sensitivity Analysis for Sample Size versus Half-Width (Precision)-
Two-Sided 95% Confidence Interval (For Number of Sites)

[figure not shown]
Sample Size	Actual Distance from Mean		
	Difference to Lin	nits (Precision)	
	SD=0.5	SD=1.0	
10	0.358	0.715	
11	0.336	0.672	
12	0.318	0.635	
13	0.302	0.604	
14	0.289	0.577	
15	0.277	0.554	
16	0.266	0.533	
17	0.257	0.514	
18	0.249	0.497	
19	0.241	0.482	
20	0.234	0.468	

A sample size of 27 providers, per arm, produces a two-sided 95% confidence interval with a distance from the mean paired difference to the limits (half-width) that is equal to 0.396 when the estimated standard deviation of the paired differences is 1.0.

Table 13Sensitivity Analysis for Sample Size versus Half-Width (Precision)-
Two-Sided 95% Confidence Interval (for Number of Providers)

Sample Size	Actual Distance	from Mean
Campic Olze	Difference to Lin	
	SD=0.5	SD=1.0
21	0.228	0.455
22	0.222	0.443
23	0.216	0.432
24	0.211	0.422
25	0.206	0.413
26	0.202	0.404
27	0.198	0.396
28	0.194	0.388
29	0.190	0.380
30	0.187	0.373

[figure not shown]
Sample Size for Patient Population

A sample size of 225 patient subjects per implementation strategy group produces a twosided 95% confidence interval with a distance from the mean paired difference to the limits that is equal to 0.131 when the estimated standard deviation of the paired difference is 1.

Sample Size	Actual Distance Difference to Lin SD=0.5	
100	0.099	0.198
125	0.089	0.177
150	0.081	0.161
175	0.075	0.149
200	0.070	0.139
225	0.066	0.131
250	0.062	0.125

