9.4.1. Primary Endpoint(s)

[figure not shown]
Endpoint	Statistical Analysis Methods
Staff Study Participants (SSP): Change from baseline at Month 12 in Acceptability of Intervention Measure (AIM), Intervention Appropriateness Measure (IAM), and Feasibility of Intervention Measure (FIM)	Acceptability of Implementation Measure (AIM), Implementation Appropriateness Measure (IAM), and Feasibility of Implementation Measure (FIM) will be summarized using descriptive statistics including 95% confidence intervals. Data will be summarized by month of study/injection visit and by implementation strategy as actual values and change from baseline. Mean AIM, IAM and FIM scores will be compared between the two implementation arms. In addition, distribution of AIM, IAM and FIM items scores will also be compared. P-values will be reported for these comparisons.
	Responses will also be summarized overall and by site type. Exploratory analyses will be undertaken to assess the variability of responses by factors including but not limited to site type, setting and for subject level outcomes markers of demographic and baseline characteristics.

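### The staff primary endpoint is change from baseline at Month 12, but the hypothesis and the 72%-86% power are for raw mean scores, so the stated power fits the endpoint only at a baseline-to-Month 12 correlation of 0.5

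*SAP*

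**What the plan says.** - **Endpoint.** Protocol 9.4.1 gives the staff primary endpoint as "Change from baseline at Month 12 in Acceptability of Intervention Measure (AIM)", with IAM and FIM alongside. The objectives tables (Protocol 1.1 and 3, SAP 2.2) also describe it as change over time through Month 12.
- **Hypothesis.** Protocol 9.1 states that the enhanced strategy is "superior than the standard implementation strategy in terms of mean staff study participant (SSP) AIM/IAM/FIM scores". SAP 2.4 repeats this. Neither names a time point or mentions change.
- **Planned comparison.** Protocol 9.4.1 says "Mean AIM, IAM and FIM scores will be compared between the two implementation arms". Actual values and changes are both to be summarised by arm, but the text does not say which of them the p-value tests.
- **Power.** Protocol 9.2 (Tables 10 and 11) and SAP 2.4.1.1 (Tables A and B) give "the power to detect a difference of 0.5 between the implementation arms in terms of AIM, IAM and FIM". The SDs are 0.61, 0.59 and 0.71, from the raw Month 4 scores of 24 staff in the US study (table title: "Staff Study Participants Scores at Month 4 in CUSTOMIZE (209493"). The footnote reads "Power calculation using two-sided t-test assuming equal variance".
- **Precision.** The same section gives confidence-interval half-widths for mean paired differences. For 27 providers the half-width is "equal to 0.396 when the estimated standard deviation of the paired differences is 1.0". Tables 12 and 13 also carry an SD of 0.5. No source is given for either value.

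**The concern.** One primary objective carries two different quantities: a change score in the endpoint column, and a raw score in the hypothesis and power table. Their variances differ unless the baseline-to-follow-up correlation takes one particular value. The documents give neither that correlation nor an estimated SD of change.

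Two things are at stake. First, the 72%-86% cannot be read as the power for the endpoint as defined. Second, the comparison could be made on the Month 12 score, on the change, or on a baseline-adjusted score. Without a stated choice, it stays open until the data are in hand.

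There is reason to doubt that the correlation is high. Protocol 4.2.5 asks staff at Month 1 about their expectations of giving the injection, and at later surveys about their experience of it.

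**Working it through.** **Inputs.** Difference 0.5, two-sided alpha 0.05, 27 per arm, SDs 0.61 (AIM), 0.59 (IAM) and 0.71 (FIM), all from Protocol 9.2, Tables 10 and 11. The correlation r is not in the documents, so a range of 0.2 to 0.7 is assumed. Baseline and Month 12 SDs are both assumed equal to the Month 4 SD. Clustering by site is ignored, as it is in Table 11.

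**Step 1: reproduce the plan's figures.** Two-sample t-test, 52 degrees of freedom, non-centrality 0.5 / (SD × √(2/27)). For AIM this is 0.5 / (0.61 × 0.272) = 3.01. Power is 84.0% (AIM), 86.3% (IAM) and 71.9% (FIM), against 84%, 86% and 72% stated. At 36 per arm it is 92.9%, 94.4% and 83.8%, against 93%, 94% and 84%. Table 11 is correct for a raw-score comparison.

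**Step 2: move to the change score.** SD of change = SD × √(2(1 − r)), which equals the raw SD only when r = 0.5. For AIM at r = 0.2 it is 0.61 × √1.6 = 0.772. For FIM at r = 0.2 it is 0.71 × √1.6 = 0.898.

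**Step 3: move to the Month 12 score adjusted for Month 1.** Residual SD = SD × √(1 − r²). For AIM at r = 0.5 it is 0.61 × √0.75 = 0.528.

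Power at 27 per arm:

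| r | AIM change | IAM change | FIM change | AIM adjusted | IAM adjusted | FIM adjusted |
|---|---|---|---|---|---|---|
| 0.2 | 65% | 68% | 52% | 85% | 88% | 74% |
| 0.3 | 70% | 73% | 57% | 87% | 89% | 76% |
| 0.5 | 84% | 86% | 72% | 93% | 94% | 83% |
| 0.7 | 97% | 98% | 91% | 99% | 99% | 94% |

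**Step 4: place the precision tables' SDs.** The half-width at n = 27 is t(0.975, 26) × SD/√27 = 2.056 × SD/5.196. This gives 0.198 at SD 0.5 and 0.396 at SD 1.0, as in Table 13. Used as an SD of change in the Step 1 calculation, 0.5 gives 95.0% power and 1.0 gives 43.8%. Solving SD × √(2(1 − r)) = 1.0 gives r = −0.34 (AIM), −0.44 (IAM) and 0.01 (FIM). Solving for 0.5 gives r = 0.66, 0.64 and 0.75.

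**The case against.** The strongest defence is that the power does match the test. The hypothesis is "in terms of mean staff study participant (SSP) AIM/IAM/FIM scores", the comparison sentence in 9.4.1 is on mean scores, and SAP 2.4.1.1 ties the power to the primary hypothesis. The amendment history shows the hypothesis, the power table and the arm comparison arriving together. On that reading, a raw-score SD is right and only the endpoint label needs attention. This stands as far as it goes: Table 11 is not miscalculated, and it fits the hypothesis as worded. It does not fit the endpoint as worded, and both are in the plan.

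A reader might infer from the precision text that the section assumes an SD of change of 1.0, so that true power is 44%. The documents do not support that. Tables 12 and 13 are titled as sensitivity analyses and set 0.5 beside 1.0. An SD of 1.0 needs a zero or negative correlation given the Table 10 SDs, so 44% is a worst case. Nor do those tables contradict Table 11: they concern precision of a mean paired difference, not an arm comparison of raw scores.

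A reader might also infer that every staff member has a usable baseline, so that adjustment costs nothing. Protocol 4.3.2 allows replacement staff, who may join after Month 1. Protocol Table 2 requires the Month 1 questionnaire only before the site's first injection, while the enhanced arm's SWAT meeting and CQI introduction fall within four weeks of site activation. Some Month 1 scores may therefore follow exposure to the enhanced arm, and adjusting for them could remove part of its effect.

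Finally, SAP 2.4 and 3 leave the survey analysis to a separate plan that is not among the documents reviewed. That plan may name the model, but it does not reconcile the protocol's own endpoint, hypothesis and power.

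**Conclusion.** The endpoint, hypothesis and power calculation do not describe one quantity. The stated 72%-86% applies to a raw-score comparison. It applies to the change endpoint only if the correlation is 0.5, an assumption the documents do not make. Over correlations of 0.2 to 0.7, the lowest change-score power across the three scales is 52% (FIM at 0.2) and the highest is 98% (IAM at 0.7). At 0.5 nothing changes, and above it the stated power is conservative.

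The size rests on equal variances at the two time points, on Month 4 SDs from 24 staff in another study carrying over to Month 12, and on independence within sites. Under these assumptions a baseline-adjusted comparison has at least as much power as either alternative, apart from one degree of freedom. That advantage requires a Month 1 score that precedes the enhanced-arm activities. This should be corrected, but it does not show that the trial is underpowered.

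**What to change.** 1. Name one primary contrast: the arm difference in Month 12 score, adjusted for the participant's Month 1 score, with site as the cluster.
2. Word Protocol 9.1 and 9.4.1, SAP 2.4 and the separate survey analysis plan to that contrast.
3. Restate Table 11 (SAP Table B) for it over a stated correlation range, for example 0.2 to 0.7, saying that the correlation is assumed.
4. State how staff with no Month 1 score, including replacements, enter the analysis.
5. Require the Month 1 questionnaire before the enhanced arm's SWAT meeting and CQI introduction, or flag scores taken afterwards and examine their influence.

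The cost is wording in a few sections, one recomputed table and a missing-baseline rule. No new instrument or visit is needed. Item 5 constrains questionnaire timing at enhanced-arm sites or, where that timing has already passed, needs a flag based on the dates of the questionnaire and the meeting.

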2.4.1.2. Sample Size for Provider Population

An overall average number of 9 sites, per arm (18 sites), would produce a two-sided 95% confidence interval with a distance from the mean paired difference (e.g. site level mean change from baseline in AIM, IAM or FIM score) to the limits (half-width) that is equal to 0.497 when the estimated standard deviation of the paired differences is 1.0, across sites.

**Table C Sensitivity Analysis for Sample Size versus Half-Width (Precision)-
Two-Sided 95% Confidence Interval (For Number of Sites)**

Sample Size	Actual Distance from Mean Difference to Limits (Precision)	
	SD=0.5	SD=1.0
10	0.358	0.715
11	0.336	0.672
12	0.318	0.635
13	0.302	0.604
14	0.289	0.577
15	0.277	0.554
16	0.266	0.533
17	0.257	0.514
18	0.249	0.497
19	0.241	0.482
20	0.234	0.468

A sample size of 27 providers, per arm, produces a two-sided 95% confidence interval with a distance from the mean paired difference to the limits (half-width) that is equal to 0.396 when the estimated standard deviation of the paired differences is 1.0.

**Table D Sensitivity Analysis for Sample Size versus Half-Width (Precision)-
Two-Sided 95% Confidence Interval (for Number of Providers)**

Sample Size	Actual Distance from Mean Difference to Limits (Precision)	
	SD=0.5	SD=1.0
21	0.228	0.455
22	0.222	0.443
23	0.216	0.432
24	0.211	0.422
25	0.206	0.413
26	0.202	0.404
27	0.198	0.396
28	0.194	0.388
29	0.190	0.380
30	0.187	0.373

[figure not shown]

Figure A Sensitivity Analysis for Sample Size versus Half-Width (Precision)-Two-Sided 95% Confidence Interval (for Sites and Providers)

2.4.1.3. Sample Size for Patient Population

A sample size of 225 patient subjects per implementation strategy group produces a two-sided 95% confidence interval with a distance from the mean paired difference to the limits that is equal to 0.131 when the estimated standard deviation of the paired difference is 1.

Table E Sensitivity Analysis for Sample Size versus Half-Width (Precision)-Two-Sided 95% Confidence Interval (for Patients)

Sample Size	Actual Distance from Mean Difference to Limits (Precision)	
	SD=0.5	SD=1.0
100	0.099	0.198
125	0.089	0.177
150	0.081	0.161
175	0.075	0.149
200	0.070	0.139
225	0.066	0.131
250	0.062	0.125

[figure not shown]
[figure not shown]

Figure B Sensitivity Analysis for Sample Size versus Half-Width (Mean Diff to Limit) versus Sample Size - Patients (Multiple Confidence Levels)

As explained in the protocol, launching CAB LA + RPV LA in the real world may present challenges that were not observed in a clinical trial setting. Therefore, in addition to the primary analyses which focuses on study staff participants data, statistical analyses of patient outcome endpoints will be performed to evaluate changes in study patients' satisfaction score results, to allow an informal comparison between the two implementation strategies.

CCI

3. PLANNED ANALYSES

This RAP describes standard analyses that will be applied to descriptively summarize clinical adverse events, laboratory evaluations, virologic parameters and other clinical safety and efficacy outcomes.

Details pertaining to reporting of survey/interview data and health outcomes/effectiveness analyses will be described in a separate analysis plan provided by Evidera or other CRO partner under GSK's oversight.

At least three analyses will be conducted to evaluate primary and secondary objectives of the protocol; an interim analysis after 50% of subjects have received their 3rd injection, and interim analysis after 100% of subjects have received their 3rd injection, and finally the primary analysis at Month 12. Further data cuts and analyses may be conducted as necessary, in order to support for internal use and publications.

A final end-of-study (EOS) analysis will be conducted when all subjects have completed the study.

3.1. Interim Analyses

As mentioned previously, interim analyses will be performed when 50% and 100% of subjects have received their 3rd injection. No formal criteria for stopping or amending the study based on the interim analysis are envisioned. Further interim analyses may be planned for publication data.

3.2. Final Analyses

The planned Month 12 primary analysis will be performed after the completion of the following sequential steps:

- All participants have completed Month 12 of the study as defined in the protocol, including any required re-tests.
- All required database cleaning activities have been completed and final database release (DBR) and database freeze (DBF) has been declared by Data Management.

4. ANALYSIS POPULATIONS

This RAP defines patient study participants in detail. Analysis populations that pertain to implementation science deliverables are documented in the Evidera SAP.

Population	Definition / Criteria	Analyses Evaluated
All Subjects Screened Population	
 All participants who were screened for eligibility and inclusion in the study 	
 Patient Study Population
Enrolled Population	
 All patient study participants who passed screening and entered the study. 	
 Patient Study Population
Safety	
 All enrolled participants who received at least one dose of CAB + RPV Oral or CAB LA + RPV LA. 	
 Patient Study Population, Safety, Efficacy, Virology, Other Assessments
Long Term Follow-up Population	
 All subjects receiving at least one dose of CAB LA and/or RPV LA who have discontinued CAB LA +RPV LA regimen and have at least one Long Term Follow-up phase clinic visit 	
 Efficacy, Safety

Refer to [Appendix 12](#): List of Data Displays which details the population used for each display.

4.1. Protocol Deviations

Important protocol deviations (including deviations related to study inclusion/exclusion criteria, conduct of the trial, patient management or patient assessment) will be summarised and listed.

Protocol deviations will be tracked by the study team throughout the conduct of the study in accordance with the Protocol Deviation Management Plan [25NOV2020 v2.0].

- Data will be reviewed prior to freezing the database to ensure all important deviations are captured and categorised on the protocol deviations dataset.
- This dataset will be the basis for the summaries and listings of protocol deviations.

A separate summary and listing of all inclusion/exclusion criteria deviations will also be provided. This summary will be based on data as recorded on the inclusion/exclusion page of the eCRF.

Protocol deviations related to the implementation process, and not the clinical conduct of the study will be reported separately. The identification and categorization of PDs as important may be different for implementation PDs vs those associated with the clinical conduct of the study.

5. CONSIDERATIONS FOR DATA ANALYSES AND DATA HANDLING CONVENTIONS

5.1. Study Treatment & Sub-group Display Descriptors

Treatment Group Descriptions		
Data Displays for Reporting		
Description	Order in TLF	Analysis
CAB Oral +RPV Oral	1	OLI Safety
CAB LA +RPV LA (includes both QM and Q2M dosing)	1	Study Population, Efficacy, Safety

5.2. Baseline Definitions

For all endpoints the baseline value will be the latest pre-dose assessment with a non-missing value, including those from unscheduled visits. If time is not collected, Day 1 assessments are assumed to be taken prior to first dose and used as baseline.

Unless otherwise stated, if baseline data is missing no derivation will be performed and baseline will be set to missing.

5.3. Multicentre Studies

In this multicentre, European-based study, enrolment and demographics will be presented by investigator site.

Exploratory analyses will be considered only if applicable.

5.4. Examination of Covariates, Other Strata and Subgroups

5.4.1. Covariates and Other Strata

The list of covariates and other strata may be used in descriptive summaries and statistical analyses, some of which may also be used for subgroup analyses. Additional covariates and other strata of clinical interest may also be considered.

Category	Details
Covariates	Implementation strategy, Site, Country, Gender, Age Group, Race, CD4 Count

